We will evaluate the impact of DHP's quality improvement pilot program (called, *Nurture*), which included nutrition education and food support offered to a subset of pregnant women aged 30 years and above and were covered by the Medicaid Managed

Care Organization (MCO) plan in their “STAR” and “CHIP” programs during October 2022 and July 2023.

From this population, DHP randomly selected a subset of approximately 500 women during that period, from which approximately 200 were in the program, the “exposed group.” The women who were covered during the same period but were not selected were not exposed to the program and will compose the “comparison group.”

The objective is to compare maternal and neonatal outcomes between those who participated in the program (exposed group) and those who did not (comparison group).

Analysis Plan:

Claims data will be pulled retrospectively from the insurer's database and other administrative sources. Information will include healthcare utilization, maternal outcomes during pregnancy, and neonatal outcomes at and post-delivery. The primary analysis involves comparing the outcomes of the exposed group with the comparison group. Statistical methods appropriate for this type of administrative data will be employed to assess the differences between the two groups, adjusting for potential confounders.

The *Nurture* program’s impact will be evaluated using claims data received from DHP concerning two composite outcomes: adverse maternal health outcomes (Composite 1) and adverse neonatal outcomes (Composite 2), as shown in Table 1 below. In addition, we will explore single outcomes, such as delivery mode (vaginal vs c-section), cost data, and birthweight, adding nuance to our understanding of the program's impact.

We will primarily use logistic regressions to predict the primary, binary composite outcomes for mothers and newborns, adjusted for risk factors such as maternal age, gestational age at the time of enrollment, pre-existing diabetes, hypertension, and being overweight pre-pregnancy (shown in Table 2). The program “dose” variables are anticipated to be continuous predictors that include both ‘usual care’ (i.e., prenatal care visits) and *Nurture* program elements (the dollar value of the gift cards spent up to 30 days after stopping the program, total number of nutrition consult minutes); see Table 3.

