Members of the Driscoll Health Plan could be enrolled in the program if they were pregnant and aged 30 years or older at the time of DHP enrollment.

15 **Total Sample Size**

To input text click in the light grey area below.

We expect to receive data from approximately 1700 DHP members broken down as the following (approximate numbers):

- Exposed group: DHP selected 511 members between October 2022 and July 2023, of whom 224 were contacted and opted into the Nurture program.
 - CHWs could not reach the remaining 287 women on the list and, therefore, could not confirm address and book consultations. We will receive the demographic data on this group to explore how they compare with the other two groups in terms of their population descriptors (Table 2 in section 3).
- Comparison group: approximately 1200 women who were 30 years old or older and pregnant during the same enrollment period and were not selected during the DHP's enrollment process.

16 Sample Size Rationale

Provide justification for the sample size and its adequacy for answering the research question.

To input text click in the light grey area below.

Data coming from claims are mostly binary, which is characterized by limited variability and increased uncertainty in proportions. This fact makes detecting statistically significant differences more challenging, requiring larger sample sizes to ensure the reliability of the findings in such studies using these binary outcomes—which is the case of Nurture.

Statistical power is critically dependent on the base rate of the outcome metrics among the comparison subjects. But, when the comparison group is composed of unmatched subjects that is at least four times the size of the exposure group, statistical power tends to be maximized.

That being said, the analysis needs to include all women as described in the previous section.

Because we do not know the incidence rate of the outcomes of interest, we estimated the effect sizes we can capture at 80% power with $\alpha = 0.05$ assuming different rates among comparison subjects (30% and 35%) and four different rates among exposed subjects (25%, 23%, 20%, 18%).

Table 4 demonstrates the statistical power to detect differences between the exposed and comparison groups, assuming *Nurture* produces certain effects. If the composite outcome rate is around 30% among comparison subjects, we have enough power to

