detect rates of 20% or lower among exposed subjects (yellow highlight). If the rate is closer to 35% among comparison subjects, we have enough power to detect rates of 25% or lower among exposed subjects (blue highlight).

Table 4. Statistical power at alpha = 0.05 to detect the program effects of interest assuming two different base rates among comparison subjects.

		% rate among exposed			
		25%	23%	20%	18%
% rate among comparison subjects	35%	78	90	98	99
	30%	28	46	80	93

17 Confidentiality and Data Security Plan

Describe how you will protect confidentiality of the subjects and the security of the data or specimens. Describe where you will store the data or specimens, who will have access to data or specimens; and the data and specimen retention and destruction timelines.

To input text click in the light grey area below.

DHP's data analysis team will anonymize and remove all PHI from all data sets prior to sharing in a way so that no information can be linked back to the individuals.

Data for analysis will be saved as Excel files and, subsequently, in formats specific for analyses using specialized statistical software, in a UT Box folder accessible only to team members involved in the data analysis, such as the PI and the biostatistician.

Data sets will be destroyed (permanently deleted) 3 years after all analyses are completed.

WAIVER OF INFORMED CONSENT

Complete this section if you are seeking a waiver of informed consent for the collection of identifiable data or biospecimens.

To approve a waiver or alteration of informed consent all of the following criteria below must be justified by the researcher.

Only complete the sections below if requesting a waiver of informed consent for the use of readily identifiable data or specimens and the data use is not regulated by HIPAA.

If research solely involves HIPAA protected data, skip this section and complete the Waiver of HIPAA Authorization section below.

18 The research involves no more than minimal risk to the subjects.

To input text click in the light grey area below. Provide protocol specific rationale as to how this study meets this requirement.

19 The waiver or alteration will not adversely affect the rights and welfare of the subjects.

To input text click in the light grey area below. Provide protocol specific rationale as to how this study meets this requirement.

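### Table 4 understates power at the plan's own group sizes (224 v 1200), and the text claims enough power for a cell printed as 78 against an 80% criterion

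*Combined protocol and SAP*

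**What the plan says.** Section 16 (Sample Size Rationale) sets its criterion with the words "we estimated the effect sizes we can capture at 80% power with" alpha 0.05. It assumes comparison-group rates of 30% and 35% and exposed-group rates of 25%, 23%, 20% and 18%. The results are in Table 4, captioned "Statistical power at alpha = 0.05 to detect the program effects of interest assuming two different base rates among comparison subjects":

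| Comparison rate | Exposed 25% | 23% | 20% | 18% |
|---|---|---|---|---|
| 35% | 78 | 90 | 98 | 99 |
| 30% | 28 | 46 | 80 | 93 |

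The text draws two conclusions. At a 30% comparison rate, power is adequate for an exposed rate of 20% or below. For the other row: "If the rate is closer to 35% among comparison subjects, we have enough power to detect rates of 25% or lower among exposed subjects".

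Neither the table nor section 16 gives the group sizes, the test or the sidedness. Sizes appear elsewhere. Section 15 (Total Sample Size) reports 511 women selected, "of whom 224 were contacted and opted into the Nurture program", and a comparison group of "approximately 1200 women who were 30 years old or older and pregnant during the same enrollment period and were not selected". Section 3 gives a rounder exposed count: "from which approximately 200 were in the program". Section 16 also remarks that power is close to its maximum when the comparison group is "at least four times the size of the exposure group", and it requires the analysis to take in everyone described in section 15.

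**The concern.** There are two separate problems.

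The first needs no calculation. The plan's line is 80%, the printed power for 35% v 25% is 78, and the text calls that enough. In the 30% row the conclusion rests on a printed 80, so the same line is met in one row and missed in the other.

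The second is that the printed values do not follow from the sample the plan says it will analyse. Table 4 is the plan's only quantified statement of what the evaluation can detect. If its inputs are unnamed and its values do not match section 15, a reader cannot tell which sample it describes, or whether the 35% v 25% statement is true.

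**Working it through.** **Inputs.** Alpha 0.05, the 80% criterion and the outcome rates are from section 16. The sizes n₁ = 224 and n₂ = 1200 are from section 15. Two-sided testing is my assumption, because the plan is silent.

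**Formula (pooled two-proportion z test).** With p₁ the exposed rate, p₂ the comparison rate and p̄ = (n₁p₁ + n₂p₂)/(n₁ + n₂):

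- SE₀ = √[p̄(1 − p̄)(1/n₁ + 1/n₂)]
- SE₁ = √[p₁(1 − p₁)/n₁ + p₂(1 − p₂)/n₂]
- Power ≈ Φ[(|p₁ − p₂| − 1.96·SE₀)/SE₁]

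**Three cells in full, at 224 v 1200.**

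- 35% v 25%: p̄ = 0.3343, SE₀ = 0.03434, SE₁ = 0.03204. (0.10 − 0.0673)/0.03204 = 1.021, power 84.6% (printed 78).
- 30% v 23%: p̄ = 0.2890, SE₀ = 0.03299, SE₁ = 0.03107. (0.07 − 0.0647)/0.03107 = 0.172, power 56.8% (printed 46).
- 30% v 20%: p̄ = 0.2843, SE₀ = 0.03283, SE₁ = 0.02982. (0.10 − 0.0643)/0.02982 = 1.196, power 88.4% (printed 80).

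**All eight cells at 224 v 1200.**

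| | 35/25 | 35/23 | 35/20 | 35/18 | 30/25 | 30/23 | 30/20 | 30/18 |
|---|---|---|---|---|---|---|---|---|
| Printed | 78 | 90 | 98 | 99 | 28 | 46 | 80 | 93 |
| Pooled z | 84.6 | 95.4 | 99.7 | 100.0 | 32.0 | 56.8 | 88.4 | 97.3 |
| Pooled minus printed | +6.6 | +5.4 | +1.7 | +1.0 | +4.0 | +10.8 | +8.4 | +4.3 |
| Exact, chi-square test | 84.7 | 95.3 | 99.7 | 100.0 | 32.4 | 57.3 | 88.4 | 97.2 |
| Log-odds Wald | 82.5 | 93.4 | 99.1 | 99.8 | 32.6 | 56.1 | 85.5 | 95.1 |
| Continuity-corrected | 82.6 | 94.6 | 99.6 | 100.0 | 29.1 | 53.4 | 86.6 | 96.7 |

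By the pooled test, six cells are more than 2 points above the printed value. Log-odds Wald also misses six, by 2.1 to 10.1. The continuity-corrected test misses five, by 3.7 to 7.4. Every two-sided 0.05 method tried gives more power than printed in all eight cells. One-sided testing fits worse (91.3 for 35/25, 69.4 for 30/23).

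**Could the table come from other sizes in the text?**

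| Sizes and test | 35/25 | 35/23 | 35/20 | 35/18 | 30/25 | 30/23 | 30/20 | 30/18 |
|---|---|---|---|---|---|---|---|---|
| Printed | 78 | 90 | 98 | 99 | 28 | 46 | 80 | 93 |
| 200 v 1200 pooled | 80.9 | 93.4 | 99.4 | 99.9 | 29.4 | 52.5 | 85.0 | 95.9 |
| 200 v 1200 log-odds | 78.6 | 91.0 | 98.4 | 99.6 | 30.0 | 52.1 | 81.9 | 93.0 |
| 200 v 800 pooled | 78.1 | 91.7 | 99.1 | 99.9 | 27.9 | 50.0 | 82.5 | 94.6 |
| 200 v 800 log-odds | 76.2 | 89.4 | 97.9 | 99.5 | 28.5 | 49.7 | 79.8 | 91.8 |
| 200 v 800 corrected | 75.4 | 90.2 | 98.8 | 99.8 | 24.9 | 46.3 | 79.9 | 93.4 |
| 200 v 800 exact Fisher | 77.2 | 91.0 | 98.9 | 99.8 | 26.7 | 48.6 | 81.3 | 93.9 |
| 224 v 896 pooled | 82.7 | 94.4 | 99.6 | 100.0 | 30.8 | 54.8 | 86.7 | 96.6 |

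The closest are 200 v 800 by log-odds and by Fisher, each with only 30/23 out (by 3.7 and 2.6). None has all eight cells within 2 points. By the pooled test, 176 v 1200 does (76.2/90.5/98.9/99.9; 26.6/47.8/80.6/93.7, largest gap 1.8), but the plan states no such size. With 1200 comparison women, the printed 28 needs 184 to 192 exposed and the printed 46 needs 165 to 169, so no single exposed size gives every printed integer.

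**Margin for the two claims (pooled).** Shrinking both groups in proportion, 35/25 stays at 80% down to about 89% of the section 15 sizes (199 v 1068), and 30/20 down to about 81% (181 v 972).

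**The case against.** The strongest objection is that Table 4 names no sizes, so *understated* is true only against 224 v 1200. Section 3 offers a second exposed count of about 200, and section 16 mentions a 4:1 ratio. With 200 v 800 and a suitable test, seven of eight cells fall within 2 points and the eighth is about 3 to 4 points out. Smaller rounded inputs with an unstated test are therefore a more likely cause than a wrong formula. The cell count and range also depend on the test.

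Much of this stands. The gap of 4 to 11 points belongs to the pooled test at 224 v 1200, and the origin of the printed figures cannot be settled from the document. But section 16 itself says the analysis must include the whole section 15 sample, so 224 v 1200 is the sample the table ought to describe, whatever produced it. Nor does the objection touch the 78-against-80 contradiction.

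A second objection is that calling the error conservative goes too far, because the planned primary analysis is different: "We will primarily use logistic regressions to predict the primary, binary composite outcomes for mothers and newborns, adjusted for risk factors", with continuous dose predictors. That also stands. Neither Table 4 nor this recalculation gives the power of that model, so the label covers the unadjusted two-group comparison only.

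**Conclusion.** The point holds, as a minor reporting error. The 35% v 25% sentence contradicts the printed 78 under the plan's own 80% criterion. At 224 v 1200, with a two-sided 0.05 pooled test, six of eight cells are printed too low, by 6.6, 5.4, 4.0, 10.8, 8.4 and 4.3 points. The largest gap (30% v 23%) is in a cell for which the text claims nothing.

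The check does not show an underpowered study. At the section 15 sizes, 35% v 25% has 84.6% power (82.5% on the log-odds scale) and 30% v 20% has 88.4% (85.5%), so both conclusions in the text are true there. At 200 v 1200, however, 35% v 25% has 80.9% by the pooled test and 78.6% by log-odds. The claim then turns on inputs the plan does not name.

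These results assume two-sided testing, take the approximate section 15 sizes as exact, and make no allowance for covariate adjustment or missing data.

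**What to change.** Replace Table 4 with values for 224 exposed v 1200 comparison women, and name the sizes, the test (unadjusted two-proportion) and the sidedness (two-sided 0.05):

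| Comparison rate | Exposed 25% | 23% | 20% | 18% |
|---|---|---|---|---|
| 35% | 85 | 95 | >99 | >99 |
| 30% | 32 | 57 | 88 | 97 |

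The 35% v 25% sentence then agrees with the table. If a smaller effective sample was meant, for example as an allowance for covariate adjustment in the logistic model, state that size and its reason, recompute, and make the sentence match the result.

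The cost is one table and one sentence, with no new data and no change to enrolment or analysis. The one drawback is that the replacement values make no allowance for adjustment, so the table should be labelled unadjusted.
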